## **10.2 Device-Associated Adverse Events**

### **10.2.1 Definition of an unanticipated adverse device effect (UADE) event**

A UADE event, as defined by cGCP guidelines, is any SAE, life-threatening problem, or death caused by or associated with a device (or with the process of evaluating a device) if that SAE, problem, or death was not previously identified in nature, severity, or degree of incidence in the investigational plan or application (including a supplementary plan or application), or any other unanticipated, serious, device-associated problem that relates to the rights, safety, or welfare of subjects or operators using the investigational product system or the comparator product system.

### **10.2.2 Reporting of device-associated adverse events**

Monitoring of adverse events (AEs) is critical to the patient's safety (i.e., human subjects protection) and data integrity.

Per this investigational plan, study subjects are not expected to experience any device-associated adverse events.

If instrument operators or research staff employed by the Sponsor experience any adverse events associated with study-specific use of the investigational device, the events will be processed according to the standard complaint investigation and handling policies, which may include recording of the event in the product's design history file.

# **11 RISK ANALYSIS**

## **11.1 Potential Risks of the Investigational Product and Clinical Investigation**

The procedures used in this study are experimental. However, there is no more of a risk during this study than there would be during any other cavity preparations performed by [name]. If you are having any pain during the procedure, we ask that you please signal us by raising your hand. We will stop the procedure and use injection anesthesia as an option to finish the procedure. You may decline to answer any or all questions and you may terminate your involvement at any time if you choose with no penalty.

## **11.2 Potential Benefits of the Investigational Product and Clinical Investigation**

Subjects are expected to benefit in the way of having better care for their teeth over going to your average dentist. One of the main benefits of using Lasers is pain reduction and anti-inflammation.

The studies made possible by the data collected in this study are expected to prove the phenomenon of laser analgesia.

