## 3 STUDY OBJECTIVES

The principal objective of this study is to prove the phenomenon of laser analgesia. Traditionally before a cavity preparation is performed, the doctor will use local anesthetic (Needle Injection) before using rotary instrument to do a cavity preparation. The study involves using the Er,Cr=YSGG Laser to perform cavity preparation without giving any injection anesthesia. VAS (Visual Analog Scale) will be used to have patients rate the laser

cavity preparation procedure to show there is laser analgesia. On each patient subject that has two similar size cavities of the same classification, either Class I or Class V, on similar teeth. Two different laser protocols will be used. One includes Low Level Laser Therapy (LLLT) to condition the pulp producing analgesia before using higher power to perform the cavity prep. The other protocol will skip the LLLT setting and prepare the cavity with the higher power to perform the cavity prep. The design of the study is to find out if there is laser analgesia and if LLLT makes a difference in providing better analgesia. The VAS forms from each procedure will be used to show there is laser analgesia and potentially cavity preparations can be performed by using the laser without the need to give injection anesthesia first.

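### Sections 11.1 and 11.2 treat laser pain relief as established and claim no added risk, although the study asks whether that relief exists and gives no injection first

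*Protocol*

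**What the plan says.** Protocol section 11.2 (Potential Benefits) makes three statements: "One of the main benefits of using Lasers is pain reduction and anti-inflammation"; "Subjects are expected to benefit in the way of having better care for their teeth over going to your average dentist"; and the studies that use these data "are expected to prove the phenomenon of laser analgesia". The Introduction (section 1) repeats the first of these and, in the same paragraph, gives as the study's aim to show whether laser analgesia exists.

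Section 3 states the question as open: "The design of the study is to find out if there is laser analgesia and if LLLT makes a difference in providing better analgesia". It also describes usual practice: "Traditionally before a cavity preparation is performed, the doctor will use local anesthetic (Needle Injection) before using rotary instrument to do a cavity preparation". In this study the laser preparation starts without that injection.

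Section 11.1 (Potential Risks) opens with "The procedures used in this study are experimental" and continues that "there is no more of a risk during this study than there would be during any other cavity preparations performed by" the named practitioner. It then asks the participant to raise a hand if in pain, and says that the procedure will be stopped and an injection will be available as an option. Section 11.3 calls the anticipated risk minimal.

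**The concern.** A benefit section should not present as known the effect that the trial is set up to detect. A risk section should name a harm that the protocol's own text makes foreseeable. Here the effect is pain relief, and the foreseeable harm is pain when no injection is given at the start.

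Two things are at stake. The first is the accuracy of the risk and benefit statements that the IRB reviews and that feed the consent discussion. The second is a modest threat to validity. The outcomes in section 4.1 are the patient's own VAS marks and hand raises, and a patient who expects the laser to reduce pain may report less of it.

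**Working it through.** The documents give no figure on this point, so the check compares their statements and reasons about where an expectation effect would fall.

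**1. Benefit against question.** Section 11.2 asserts pain reduction without qualification and anticipates a positive result. Section 3 asks whether the phenomenon exists. Section 2.1 cites earlier work on analgesic effects of low-level laser, but says that the claims for this laser system without injection are generally anecdotal. Nothing in the protocol supports the promise of better care than elsewhere. The conflict is within the document and needs no outside source.

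**2. Risk against design.**
- Section 3: usual practice is an injection first; the study preparation is done without it, on both teeth.
- Section 2.1: laser analgesia is described as falling short of the numbness that an injection gives.
- Sections 4.1 and 7.1: the procedure is built around pauses for pain, with up to 3 intra-operative VAS marks and an offer of anesthetic.
- Section 11.1: pain appears as something to signal, not as a risk that follows from omitting the initial injection.

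The first three items make such pain foreseeable. The fourth does not say so.

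**3. Route to the participant.** Section 5.2.1 says patients will be told of the possible risks, and section 11.1 is the protocol's statement of those risks. It is written in the second person. Section 13.2.1 has the investigator explain the whole study in lay terms, and section 13.3 sends the protocol to the IRB. The text under section 7.3 (Randomization and Blinding) covers only confidentiality. It is therefore reasonable to infer that this wording, or wording like it, reaches participants before they rate pain. The documents do not show it directly.

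**4. Where an expectation effect would land.** As a simple illustration, let the two teeth of one patient have pain m1 (with LLLT) and m2 (without), and let expectation lower the reported values by e1 and e2.
- Difference between teeth: (m1 − e1) − (m2 − e2) = (m1 − m2) − (e1 − e2). If a general belief about lasers acts equally on both teeth, e1 = e2 and the term vanishes.
- Mean level over both teeth: (m1 + m2)/2 − (e1 + e2)/2. With e1 = e2 = e, the level is too low by e, and nothing in the design removes it, because neither tooth is prepared without the laser.

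The cancellation is exact only if the effect is additive, equal on both teeth and not cut off at the zero end of the scale, so it is better described as large than as complete. The documents give no value for e.

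**The case against.** The strongest reply is that this is loose wording with little consequence. Several parts of it stand.

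- **A reader might infer that patients are not told about pain without the injection.** The documents do not support that. The consent pages are not available here, and sections 5.2.1, 6.3 and 13.2.1 provide for risk information, questions and explanation.
- **A reader might infer that section 11.1 ignores pain.** It does not: it mentions pain, the hand signal, stopping and the optional injection, and section 6.1.2 repeats that option under safety. Only the explicit link to omitting the initial injection is absent.
- **A reader might call the no-added-risk sentence plainly false.** Its comparator is the same practitioner's other preparations, and that practitioner's routine use of injection is not stated. Section 2.1 describes laser users who work without injection. Against the traditional practice in section 3 the sentence is unsupported, but it is not shown to be false.
- **A reader might argue that one suppressed hand raise turns a real rating into zero.** Section 4.1 gives an overall rating of zero only to a patient who raises no hand during the entire procedure, so this would hold only where the suppressed raise was the sole one.
- **Some instructions work the other way.** Section 4.1 tells patients to signal even slight pain and encourages them to stop the treatment.
- **Rewording does not remove the expectation.** The study title itself names laser analgesia, and the lack of a non-laser comparator remains.

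The reply does not answer the conflict between section 11.2 and section 3, or the unnamed risk in section 11.1.

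**Conclusion.** The point holds in a limited form. The benefit statements in section 11.2, and the one repeated in section 1, contradict the open question in section 3. Section 11.1 leaves unnamed a foreseeable harm that sections 2.1 and 3 imply. Both are established on the text.

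The effect on the pain ratings is an inference whose size cannot be computed. It assumes that participants hear wording like that of section 11 and that it alters what they report. If so, the absolute claim of laser analgesia is the exposed result. A reader might infer that the LLLT comparison is biased as well. The documents do not establish that, because a belief about lasers in general applies to both teeth of the same patient and may largely cancel. No estimate, analysis or sample size changes as a result of this point. It is a wording correction worth making because it is specific and nearly free.

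**What to change.** **Section 11.2.** Delete the sentence on the main benefits of lasers and the promise of better care than the average dentist, and remove the expectation that analgesia will be proved. Put in their place: *Whether the laser reduces pain is the question of this study. It is not established, and there may be no benefit.* Bring the matching sentence in section 1 into line.

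**Section 11.1.** Replace the no-added-risk sentence with: *Because no injection is given first, you may feel pain that an injection might have prevented.* Reconcile this with sections 2.1, 3 and 4.1. Leave the existing option to stop and have an injection as it is; no clinical rule changes.

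**Consent form.** Check that it says the same on both points.

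**Cost.** A text change and IRB notification. Recruitment may be slightly slower, and the pain warning may produce a small expectation effect in the opposite direction, so its wording should stay neutral. The lack of a non-laser comparator is a separate limit on the absolute claim and is not cured by this change.

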## **11.3 Minimization of Risks**

Although the risk to subjects participating in the study is anticipated to be minimal, the clinician, at his/her discretion, will not collect data from those individuals for whom collection is judged to pose an unusually high risk of physical or mental harm or discomfort.

Participation in this study poses no risk to study personnel other than that normally encountered during standard practice. These risks will be minimized by adherence to the following guidelines:

- Personnel should wear appropriate personal protective equipment to avoid contact of the eyes or skin with hazardous materials or products derived from biological sources.

# **12 INVESTIGATOR RESPONSIBILITIES**

## **12.1 Site Qualification and Study Oversight**

The PI is responsible for general administration of the study.

Before the study, the PI must:

- Obtain approval to conduct the study from the study site's IRB;
- Sign the Protocol Signature Page him/herself and have all sub-investigators sign
- Provide financial disclosures for themselves and all sub-investigators participating in study conduct, per Title 21CFR 54 (see **Section 12.4** below).

During the study, the PI must ensure that:

- The study is conducted ethically;
- Case report forms (CRFs), including Subject ICFs, are provided with each transfer of data requiring informed consent
- All other study forms are completed as instructed.

## **12.2 Case Report Forms/Electronic Data Records**

As used in this protocol, the term CRF should be understood to refer to either a paper form or an electronic data record or both, depending on the data collection method(s) used.

Original CRFs are the sole property of [name] and should not be made available in any form to third parties, except for authorized representatives of [name] or appropriate regulatory authorities.

It is the PI's responsibility to ensure completion, review, and approval of all CRFs. CRFs must be signed by the PI or by an authorized staff member. These signatures serve to attest that the information contained on the CRFs is true. At all times, the PI has final personal responsibility for the accuracy and authenticity of all clinical and laboratory data entered on the CRFs.

### **12.3 Access to Source Documents**

[name] or its agents and appropriate regulatory authorities shall be granted direct access to all study-related documents to perform verification that the protocol and all applicable current Good Laboratory Practices (cGLPs), Good Clinical Practices (GCPs), and regulations are being followed and to confirm that study documents are complete and accurate. It is important that Investigator and their relevant personnel be made available during monitoring visits and any audits or inspections, and that sufficient time is allotted for the process.

### **12.4 Financial Disclosure**

Investigators must provide sufficient, accurate financial information in accordance with local regulations. Investigators are responsible for providing information concerning their relevant financial interests during the course of the study and for 1 year after completion of the study. Conflicts of interest should be disclosed as required by law.

### **12.5 Deviations from the Study Protocol**

An Investigator may not deviate from the study protocol unless the deviations are necessary under emergency circumstances to protect the rights, safety, or well-being of human subjects or the scientific integrity of the clinical investigation. These deviations must be documented and promptly reported to Sponsor and, if applicable, to the IRB providing oversight of the study. Protocol deviations may result in corrective and preventive actions and/or disqualification of the Investigator.

### **12.6 Record Retention**

To enable evaluations and/or audits from regulatory authorities, the PI and all sub-investigators agree to retain all study records, including copies of all CRFs, all forms, and source documents, for 3 years following completion of the project dependent upon the study data.

## **12.7 Publication Policy**

The results of this study will be submitted for publication. The PI agrees that any publication of data from this study will comply with publication policy, the instructions to authors outlined by the editor of the journal or conference proceedings where the data is to be published, and the spirit of recommendations made in the good publication practice guidelines (GPP3) of the International Society of Medical Publication Professionals.

# **13 ETHICS AND COMPLIANCE**

## **13.1 Investigational Device Exemption**

Although exempt from IDE regulations as noted in Title 21 CFR 812.2(c), the conduct and performance of this study will be in accordance with applicable Sponsor and Investigator responsibilities as described in Title 21 CFR 809 and Title 21 CFR 812.

## **13.2 Informed Consent and De-Identification**

### **13.2.1 Prospectively collected data**

All subjects will be given a copy of the IRB-approved ICF to review before their study participation begins. The Investigator will explain all aspects of the study in lay language and answer all of the potential participant's questions regarding the study. If the participant decides to participate in the study, s/he will be asked to sign and date the ICF. Subjects who refuse to participate or who withdraw from the study will be treated without prejudice.

### **13.3 IRB Review**

The PI is required to obtain IRB oversight of the research study. Performance of the study may not begin until written evidence of IRB approval has been provided.

The conduct and performance of this study will be in accordance with applicable Sponsor and Investigator responsibilities as described in Title 21 CFR 812 and other Good Clinical Practice guidance.

IRB/Ethics Committee oversight will be required as human subjects or data from humans are being used. This protocol and the associated informed risks document(s) (if applicable) must be submitted to the IRB for review and approval. Performance of the study at a given site may not begin until written evidence of IRB oversight has been provided. IRB Review and approval must comply with Title 21 CFR 812 Subpart D.

## 13.4 Confidentiality of Data and Patient Records

The study institution shall keep all records associated with this study for at least 3 years, as specified in **Section 12.6**. Investigators will keep all records associated with this study for at least 3 years.

### 13.4.1 Provisions to Protect the Privacy Interests of Participants

The PI and/or study institution shall provide sufficient information to allow the IRB to evaluate the researcher's provisions to maintain the confidentiality of data.

Privacy data will be maintained in accordance with HIPAA, other applicable policies, and local law.

